5.2. Background

5.2.1. Investigational Medicinal Product: FX006

FX006 is an extended-release formulation of triamcinolone acetonide (TA) for IA administration. It is approved under the trade name ZILRETTA™ for the management of pain of osteoarthritis of the knee, however, injection in both knees has not been studied and is an investigational use. FX006 is intended to deliver TA to the synovial and peri-synovial tissues for a period of approximately 3 months depending on the dose administered. ([Bodick et al, 2013](#))

FX006 contains TA, United States Pharmacopeia (Ph. Eur/USP), formulated in 75:25 poly(lactic-co-glycolic acid) (PLGA) microspheres with a nominal drug load of 25% (w/w) and is provided as a sterile white to off-white powder for reconstitution. The drug product is reconstituted with diluent containing an isotonic, sterile aqueous solution of sodium chloride (NaCl; 0.9% w/w), carboxymethylcellulose sodium (CMC; 0.5% w/w) and polysorbate-80 (0.1% w/w) to form a suspension prior to IA injection.

Further details of the physiochemical properties of FX006 can be found in the Investigator's Brochure (IB).

5.2.2. Rationale for FX006 in OA of the Knee

Available clinical and nonclinical data indicate that FX006 is safe and well tolerated when administered as a single injection into one knee and provides pain relief that is meaningfully better and more persistent than that provided by immediate release triamcinolone acetonide (TAc). Nonclinical data and the literature suggest that this potential could extend to limiting structural progression in patients with inflammatory joint disorders. The near term clinical development program for FX006 focus on analgesics effects in patient with OA (bilateral knee, hip, and shoulder) as well as other shoulder maladies.

5.2.3. Toxicology

Overall, single or repeat administration of FX006 at the proposed clinical dose of 32 mg has no new safety liabilities compared to TAc:

- Systemic findings were similar among TAc and FX006 groups following single and repeat dosing and were generally reversible. Initial effects on clinical pathology parameters were more pronounced for the immediate-release form. The incidence and/or intensity of steroid-associated systemic histopathological findings at the later time points were slightly higher for high dose FX006 than for TAc at the same dose level of TA (18.75 mg/mL/joint), as expected based on the sustained release of TA. Microspheres were not detected in tissues outside of the synovial space.
- Local findings were similar among TAc and the FX006 groups and were reversible. The single and repeat dose dog toxicity studies recapitulated known effects of TA that had been previously published in normal animal joints following prolonged exposure. These include decreased Safranin O staining and changes in structure and cellularity of articular cartilage.
- An expected, mild, reversible Foreign Body Response (FBR) was noted to the PLGA component of FX006 microspheres.
 - The local tissue response to the presence of blank microspheres as well as FX006 microspheres consisted of an expected FBR of macrophage and multinucleated giant cell infiltration involving the synovium. Following a single dose, the FBR was evident at Day 4, peaked at approximately 6 weeks and was completely resolved by 6 months in all FX006 animals. Occasional lymphocyte and plasma cell infiltrates and sporadic focal-to-multifocal areas of minimal-to-slight fibrosis resolved by 9 months. Following repeat IA dosing, a similar local, reversible FBR was noted.
 - Further, the dogs in these studies showed no local signs of inflammation on or around the joint and did not display pain, discomfort or difficulty.

Information available for TA from the literature, corticosteroid product labels and clinical experience suggest that the potential of genetic toxicity, reproductive toxicity and carcinogenic potential of TA are well understood. Similarly, the biocompatibility and local safety of PLGA

microspheres, and genotoxic, reproductive toxicological and carcinogenic potential of PLGA have been described in a combination of literature and product information packages. Therefore, no new risks relative to TAcS are presented by FX006 as intended for use.

5.2.4. Systemic and Local PK in Patients with Osteoarthritis of the Knee

Overall, FX006 displayed a favorable plasma PK profile relative to TAcS.

PK observations resulted in a controlled and stable release of TA from PLGA microspheres into synovial tissues, where concentrations remained high relative to plasma concentrations for at least 12 weeks. TA was absorbed systemically, with a plateau in plasma TA concentrations occurring in the first 24 hours post-dose, and slow elimination from the systemic circulation observed in the weeks thereafter.

Relative to TAcS, FX006 32 mg produced substantially lower peak plasma and systemic exposure to TA. FX006 performed as expected, prolonging the residence of TA in the joint while minimizing systemic exposure to TA.

5.2.5. Pharmacodynamics in Patients with Osteoarthritis of the Knee

In a Phase 2 PK/PD study, evaluating three dose levels of FX006 (10mg, 40mg, 60mg) administered as a 3mL injection, suppression of cortisol in the days following injection produced by the 10 and 40 mg dose of FX006 was less than that produced by injection of TAcS; the 60 mg dose of FX006 produced effects similar to TAcS 40 mg. Cortisol suppression subsequent to Day 1-2 associated with all doses of FX006 would not be expected to be of clinical consequence in adult patients without otherwise compromised HPA axis function.

In a Phase 2 study in diabetic patients with knee OA, treatment with FX006 32 mg resulted in a statistically significant ($p=0.0452$) reduction in blood glucose elevation relative to TAcS over a 72-hour period following IA injection. The time in glycemic target range (70-180 mg/dL) ([American Diabetes Association, 2016](#)) was greater for FX006 as compared to TAcS over the 48 hours post IA injection, providing another indication of the improvement in glycemic control. Over the entire time course of the 15-day post injection glucose monitoring period, blood glucose levels associated with FX006 remained at levels similar to or lower than those produced by TAcS. This observation is consistent with PK studies demonstrating low systemic exposure to TA associated with FX006.

5.2.6. Efficacy in Patients with Osteoarthritis of the Knee

Efficacy data from three studies provide substantial evidence supporting the effectiveness of FX006 32 mg in the management of OA pain. ([Bodick et al, 2015](#), [Conaghan et al, 2017](#))

Results of the primary endpoint from the Phase 3, multi-center, adequate, and well-controlled trial, showed that patients treated with FX006 32 mg had a rapid, durable, and meaningful analgesic response that was statistically significantly better than placebo treated patients ($P < 0.0001$). This finding was supported by a second smaller Phase 2b study, where a highly similar pattern of response to FX006 32 mg was demonstrated.

Robustness of the primary outcome in the Phase 3 study was further supported by the internal consistency demonstrated in favor of FX006 32 mg through secondary analyses utilizing the primary outcome data average daily pain (ADP) to evaluate durability and magnitude of

response. These included least square mean (LSM) testing at each week and area under the effect curve (AUE) analyses for Weeks 1 through 12 and Weeks 1 through 24. Results demonstrated that the analgesic effect of FX006 32 mg is significant at Week 1, increases through Week 7, and is sustained through at least Week 16. Responder analyses further suggested that FX006 provides clinically relevant improvement from Weeks 1 through 16 relative to placebo.

Analyses utilizing data collected from other instruments or measures (Western Ontario and McMaster Universities Osteoarthritis Index (WOMAC), Patients' Global Impression of Change (PGIC), Clinical Global Impression of Change (CGIC), and Knee injury and Osteoarthritis Outcome Score (KOOS) Quality of Life (QOL)) provided additional insight into effects on pain relief as well as physical function and global well-being. FX006 32 mg provides clinically relevant improvement relative to placebo through Week 12 for WOMAC and KOOS QOL and through at least Week 16 for PGIC and CGIC. Additionally, significant reduction of rescue medication utilization in patients treated with FX006 32 mg is of potential important clinical consequence and adds a meaningful element to the overall effectiveness profile of FX006 32 mg. Collectively, these results provide substantial evidence to support FX006 32 mg as an effective therapy for the management of OA knee pain.

5.2.7. Systemic and Local Safety in Patients with Osteoarthritis of the Knee

The evaluation of 687 patients treated with a single IA injection of FX006 at any dose in the FX006 clinical studies suggests that it was well tolerated with systemic and local safety profiles similar to those of TAcS and placebo.

The safety data from the FX006 clinical studies are largely consistent.

- The number of treatment-emergent adverse events (TEAEs) reported was similar across groups (FX006 46.0%; placebo 49.2%; TAcS 51.0%).
- The majority of TEAEs in FX006-treated patients were mild or moderate (Grade 1 or 2). Severe or life-threatening events occurred in the FX006-treated patients at a rate of 3.0% as compared to 5.0% and 2.6% in the placebo and TAcS groups, respectively.
- In the FX006-treated patients (n=687), the most common TEAEs were:
 - Arthralgia (in any joint) 9.8% (n=67)
 - Headache 5.4% (n=37)
 - Upper Respiratory Tract Infection 3.1% (n=21)
 - Joint swelling 2.8% (n=19)
 - Contusion and back pain 2.3% (n=16)
 - Nasopharyngitis 2.2% (n=15)
- The rate of serious adverse events (SAEs) was low and consistent across groups (FX006 1.9%; placebo 1.1%; TAcS 2.3%); none were considered related to the study drug.
- Across all studies there were no deaths.

In the Phase 3 study, qualitative assessments based on X-rays of the index knee at 24 weeks post injection included joint space narrowing (JSN), subchondral bone changes, osteonecrosis, and insufficiency fracture.

- The overall rate of JSN worsening of at least 1-grade between baseline and Week 24 was low and similar among treatment groups (5.0% [7/140], 4.1% [6/148], and 3.5% [5/145] of patients with both baseline and Week 24 X-rays in the FX006 32 mg, placebo, and TAcS groups respectively); for all but 1 of these 18 patients, JSN worsened by 1 grade only. The remaining patient (in the placebo group) had a 2-grade worsening in JSN (from 0 at baseline to Grade 2 at Week 24).
- No FX006-treated patient had X-ray evidence of treatment-emergent insufficiency fracture, subchondral bone changes, or osteonecrosis at Week 24.
- Eighteen patients discontinued the study prior to Week 24 and completed a final X-ray as part of early termination visit. Of these, 2 patients, 1 in the FX006 32 mg group and 1 in the placebo group, had a 1-grade increase in JSN. There were no reports of insufficiency fracture, subchondral bone changes, or osteonecrosis.

5.2.8. Conclusion

These data provide bases for continued clinical study of FX006.

6. STUDY OBJECTIVES

6.1. Primary Objective

The primary objectives of this study are (a) to compare the systemic exposure to triamcinolone acetonide from extended-release FX006 and immediate release TAcS and (b) to assess the safety and general tolerability, when FX006 is administered as two 5 mL IA injections (one to each knee) for a total dose of 64 mg or TAcS is administered as two 1 mL injections (one to each knee) for a total dose of 80 mg in patients with bilateral knee OA.

7. INVESTIGATIONAL PLAN

7.1. Overall Study Design and Plan

This randomized, parallel group study will be conducted in male and female patients \geq 40 years of age with bilateral knee OA.

Approximately 24 patients will be randomized to one of two treatment groups (1:1) and treated with two IA injections of either:

- extended-release FX006 64 mg total dose (approximately 12 patients) or
- immediate-release TAcS 80 mg total dose (approximately 12 patients)

Each patient will be evaluated for a total of 6 weeks following the two IA injections. Following screening, PK and safety will be evaluated at 6 out-patient visits scheduled on Study Days 1 [calendar day of injection], 2, 8, 15, 29, and 43. The study is expected to enroll in approximately 1 month.

7.2. Site Staffing Requirements

The Principal Investigator is responsible for overseeing the conduct of the study at his/her site, ensuring that sufficient and appropriately experienced staff are available to conduct the trial, and ensuring that activities are appropriately delegated and documented. Any delegation of responsibilities will be documented in a study-specific Clinical Site Responsibilities and Signature log. The term 'Principal Investigator' is used throughout this protocol to refer to the actual Principal Investigator and/or his/her delegated team member(s) for the specific responsibility being described.

Pharmacist/coordinator

- must be a registered pharmacist or an individual with the qualifications and training required to handle and prepare study medications
- is responsible for handling and preparing all study medications and maintaining investigational product accountability records

Injector/Aspirator

- must be a medical doctor, a physician's assistant, or nurse practitioner experienced in administering IA injections and performing synovial fluid aspirations of the knee
- is responsible for performing IA injections of study medication and synovial fluid aspirations of the knee

Assessor

- must be a medical doctor, a physician's assistant, or nurse practitioner
- must have relevant OA experience
- responsible for performing the physical examination and knee assessments

- Assessing causality of an adverse event (AE) or SAE
 - Must be either the PI or physician sub-investigator

The same individual may serve in multiple roles (e.g., a physician sub-investigator may serve as both the Injector/Aspirator and/or Assessor).

7.3. Discussion of Study Design

7.3.1. Rationale for Study Population

Patients with pain associated with OA of the knee as defined by clinical and radiologic criteria that are otherwise in good health or that have chronic conditions (for example, hypertension) that are well controlled are included. In general this population tolerates IA injections of commercially available corticosteroids ([Habib 2009](#)). In prior clinical studies of FX006 in this population, single injections of up to 60 mg of FX006 were well tolerated. It is expected that plasma levels will increase secondary to simultaneous injections in the knee. This study is to establish the safety with these increased levels.

7.3.2. Rationale for Dose Selection

The 32 mg dose of FX006 was selected for this study based on the safety and efficacy seen for this dose in the knee. In a Phase 2b study (FX006-2014-006) comparing 16 mg and 32 mg doses, both dose levels of FX006 achieved maximal analgesic effect based on the ADP intensity score using an NRS of similar magnitude at Week 5 post-injection. However, a dose effect was evident in the maintenance of maximal effect, which persisted through Week 9 with 16 mg FX006 and through Week 13 with 32 mg FX006. The durability of the treatment effect seen with the 32 mg dose was reproduced in the Phase 3 Study FX006-2014-008.

Thus, based on the collective clinical evidence (a) there is a dose response effect and (b) the 32 mg dose FX006 appears to be the most effective of those doses studied in OA of the knee. Further, across several trials, a single IA administration of 32 mg FX006 in the knee has been shown to be well-tolerated and in PK studies a single 5 mL IA injection of 32 mg FX006 resulted in substantial and sustained joint residency of TCA in adults with OA of the knee. The approved dose of FX006 is 32 mg, therefore this dose was selected for further study in investigational uses.

7.3.3. Rationale for Study Design

The current trial is design is substantially similar to PK studies previously conducted in OA of the knee. The randomized, open label, parallel group design applied in this protocol has proved reliable for comparing the plasma PK profiles for these two different formulations.

7.3.4. Rationale for Study Parameters

Plasma drug concentration measurements directly support the objective of the study to characterize the systemic PK and local extent and duration of exposure of TA from FX006 and TAc.

The clinical safety parameters to be assessed (adverse events, physical examinations, knee examinations, vital signs, and clinical laboratory evaluations) are standard safety and tolerability assessments and support the clinical monitoring necessary based on the toxicology profile for FX006.

7.3.5. Rationale for Control Type

The active control (TAc) Kenalog®-40 Injection is commonly used in treatment of OA of the knee, and differences in systemic exposure are informative to clinicians and may be extrapolated to other corticosteroids.

7.4. Selection and Withdrawal of Study Patients

7.4.1. Number of Patients

Approximately 24 patients with bilateral knee OA (up to 12 per treatment arm) will be treated with two IA injections (one to each knee) of FX006 or TAc.

7.4.2. Inclusion Criteria

To be included in the trial, patients must fulfill the following criteria:

1. Written consent to participate in the study
2. Male or female ≥ 40 years of age
3. Symptoms consistent with OA in both knees for ≥ 6 months prior to Screening (patient reported is acceptable)
4. Currently meets ACR Criteria (clinical and radiological) for OA in both knees ([Altman et al, 1986](#)) as follows:
 - Knee pain
 - at least 1 of the following:
 - Age > 50 years
 - Stiffness < 30 minutes
 - Crepitus
 - Osteophytes
5. Knee pain in both knees for > 15 days over the last month (as reported by the patient)
6. Body mass index (BMI) ≤ 40 kg/m²
7. Morning serum cortisol result within normal range at Screening (5-23 mcg/dL or 138-635 nmol/dL)
8. Ambulatory and in good general health
9. Willing and able to comply with the study procedures and visit schedules and able to follow verbal and written instructions.

10. Willing to abstain from use of the following protocol-restricted medications during the study:
 - Intravenous (IV), Intramuscular (IM), oral, inhaled, intranasal or topical corticosteroids
 - IA corticosteroids in any joint
 - IA viscosupplementation (hyaluronic acid) in either knee
 - Any investigational drug or device
 - Immunomodulators, immunosuppressives, or chemotherapeutic agents
 - Live or live attenuated vaccines
11. Sexually active males and females of child-bearing potential (defined as not surgically sterile or post-menopausal [defined as 12 consecutive months with no menses without an alternative medical cause] for at least 1 year as documented in medical history) agree to use one of the following highly effective method of contraception: abstinence; oral, injected or implanted hormonal methods of contraception; intrauterine device or intrauterine system; condom or occlusive cap (diaphragm or cervical/vault caps) with spermicidal foam/gel/film/cream/suppository; or monogamous intercourse with a partner who is surgically sterile (post-vasectomy, post-hysterectomy, or tubal ligation.) Females must agree to use such contraceptive measures for at least 30 days after the administration of the study drug. Males must agree to use contraceptives for at least 90 days after administration of the study drug.

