7.7.3. Pharmacodynamic Variables

Blood samples for morning serum cortisol levels will be collected between 7 am and 9 am at Screening and on Study Days 1, 2, 8, 15, 29, 43. Levels observed in the two treatment arms will be compared using descriptive statistics. There is no statistical hypothesis or objective for this parameter.

Synovial fluid samples will be preserved for a maximum of 5 years for potential future analyses of biomarkers that may contribute to the pathogenesis of OA and/or be associated with responsiveness to FX006 treatment. No genomic analyses (gene sequencing studies) will be performed using these samples. Patients will be able to withdraw consent throughout the duration of storage. Once analysis has begun, consent will no longer be able to be withdrawn.

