7. CLINICAL STUDY REPORT APPENDICES

7.1. Statistical Tables to be Generated

Table 14.1.1	Patient Enrollment and Disposition
Table 14.1.2	Demographic and Baseline Characteristics (Safety Population)
Table 14.1.3	Osteoarthritis History and Bilateral Knee Characteristics (Safety Population)
Table 14.1.4	Summary of Protocol Deviations (Safety Population)
Table 14.1.5	Study Drug Exposure Summary (Safety Population)
Table 14.1.6	Summary and Change from Baseline for Serum Cortisol (nmol/L) by Visit (Safety Population)
Table 14.1.7	Plasma Drug Concentrations (pg/mL) by Time Point (PK Population)
Table 14.2.1	Plasma Pharmacokinetic Parameters (PK Population)
Table 14.2.2	Summary of Bioequivalence Geometric Mean Ratios (PK Population)
Table 14.3.1.1	Summary of Treatment-Emergent Adverse Events (Safety Population)
Table 14.3.1.2	Treatment-Emergent Adverse Events by System Organ Class and Preferred Term (Safety Population)
Table 14.3.1.3	Treatment-Emergent Adverse Events by System Organ Class and Preferred Term - Related to Study Drug (Safety Population)
Table 14.3.1.4	Treatment-Emergent Adverse Events by System Organ Class and Preferred Term by Maximum Severity (Safety Population)
Table 14.3.1.5	Knee-Related Treatment-Emergent Adverse Events by System Organ Class and Preferred Term (Safety Population)
Table 14.3.1.6	Knee Related Treatment-Emergent Adverse Events by System Organ Class and Preferred Term- Related to Study Drug (Safety Population)
Table 14.3.1.7	Knee Related Treatment-Emergent Adverse Events by System Organ Class and Preferred Term by Maximum Severity (Safety Population)
Table 14.3.1.8	Serious Adverse Events by System Organ Class and Preferred Term (Safety Population)
Table 14.3.2.1	Patient Listing of Deaths
Table 14.3.2.2	Patient Listing of Serious Adverse Events
Table 14.3.2.3	Patient Listing of Discontinuations Due to Adverse Events
Table 14.4.1.1	Summary and Change from Baseline for Hematology Parameters by Visit (Safety Population)
Table 14.4.1.2	Summary and Change from Baseline for Chemistry Parameters by Visit (Safety Population)
Table 14.4.2	Summary and Change from Baseline for Vital Signs by Visit (Safety Population)
Table 14.4.3	Summary of Bilateral Knee Assessments (Safety Population)

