7.3. Data Listings to be Generated

Listing 16.2.1	Patient Disposition
Listing 16.2.2.1	Inclusion/Exclusion Criteria Not Met
Listing 16.2.2.3	Protocol Deviations
Listing 16.2.3.1	Analysis Populations
Listing 16.2.4.1	Demographics and Baseline Characteristics
Listing 16.2.4.2	Medical History
Listing 16.2.4.3	Medical History - Knee Osteoarthritis
Listing 16.2.4.4	Medical History - Prior Treatment of Knee Osteoarthritis
Listing 16.2.4.5	Medical History - Other Osteoarthritis
Listing 16.2.4.6	Medical History - Other Osteoarthritis Procedures or Surgeries
Listing 16.2.4.7	Knee X-ray/Kellgren-Lawrence Grade
Listing 16.2.5.1	Study Drug Exposure
	Plasma Sampling Times and Plasma Drug Concentration Measurements
Listing 16.2.5.2	Plasma PK Parameters
Listing 16.2.6	Serum Cortisol (nmol/L)
Listing 16.2.7.1	Adverse Events – Sorted By Patient and Onset Date
Listing 16.2.7.2	Adverse Events Occurring in Both Knees – Sorted By Patient and Onset Date
Listing 16.2.7.3	Adverse Events – Sorted by System Organ Class, Preferred Term, Treatment, Patient, and Onset Date
Listing 16.2.7.4	Adverse Events – Glossary by MedDRA SOC, Preferred Term and Verbatim
Listing 16.2.8.1	Laboratory Assessment – Hematology
Listing 16.2.8.2	Laboratory Assessment – Chemistry
Listing 16.2.8.3	Screening Laboratory Assessments and Urine/Serum Pregnancy Test Results
Listing 16.2.8.4	Bilateral Knee Assessments
Listing 16.2.9.1	Vital Signs
Listing 16.2.9.2	Physical Examination Findings
Listing 16.2.9.3	Electrocardiograms Results
Listing 16.2.9.4	Prior and Concomitant Medications
Listing 16.2.9.5	Knee Aspiration
Listing 16.2.9.6	Surgical Procedures

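### Inclusion criterion 7 gives the morning cortisol range in two units that differ tenfold; the molar figures fit nmol/L, not the printed nmol/dL

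*Protocol*

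**What the plan says.** Criterion 7 in Protocol Section 7.4.2 reads "Morning serum cortisol result within normal range at Screening (5-23 mcg/dL or 138-635 nmol/dL"). The same criterion, with the same numbers and units, is in the inclusion criteria of the synopsis (Protocol Section 2). These are the only places in either document where cortisol is given in nmol/dL.

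The SAP uses a different molar unit. Its table list (SAP Section 7.1, Table 14.1.6) has "Summary and Change from Baseline for Serum Cortisol (nmol/L) by Visit (Safety Population"), and its listing list (SAP Section 7.3, Listing 16.2.6) has "Serum Cortisol (nmol/L"). SAP Section 4.9.2 puts clinical laboratory values in SI units.

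Morning cortisol is part of the central laboratory panel (Protocol Section 7.9.10, Table 3). It is also a descriptive pharmacodynamic measure, of which Protocol Section 7.7.3 says "There is no statistical hypothesis or objective for this parameter".

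**The concern.** A range stated in two units must describe the same set of results. Here the word joining them presents the ranges as equivalent, yet both are per decilitre, and the molar numbers are the ones expected per litre.

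The text is a numeric eligibility limit that every patient has to meet. Protocol Section 11.5 makes the investigator responsible for enrolling only eligible patients, and SAP Listing 16.2.2.1 is reserved for eligibility criteria not met. If a result is converted to nmol/dL and compared with the printed molar limits, a patient whose cortisol lies inside 5-23 mcg/dL looks far too low. That patient could be screened out or recorded as a deviation. In a trial of about 24 patients even a few such cases would be a nuisance.

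**Working it through.** **Inputs.** From Protocol Section 7.4.2 and the synopsis: 5 and 23 mcg/dL; 138 and 635 nmol/dL. From SAP Sections 7.1 and 7.3: the reporting unit nmol/L. Assumed, because the documents do not state it: cortisol molar mass M = 362.46 g/mol, with 362 and 363 also run.

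**Step 1. Try to reproduce the printed molar range.** Formula: nmol/dL = (mcg/dL × 1000) / M.
- Lower limit: 5000 / 362.46 = 13.79 nmol/dL (printed: 138).
- Upper limit: 23000 / 362.46 = 63.46 nmol/dL (printed: 635).

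The printed figures do not reproduce. Both are ten times too large for the unit shown.

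**Step 2. Convert the other way.** Formula: mcg/dL = nmol/dL × M / 1000.
- 138 × 362.46 / 1000 = 50.0 mcg/dL.
- 635 × 362.46 / 1000 = 230.2 mcg/dL.

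The molar range as printed is therefore about 50-230 mcg/dL, entirely above the 23 mcg/dL upper limit of the mass range. No single result satisfies both expressions.

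**Step 3. Repeat in the SAP's unit.** Formula: nmol/L = nmol/dL × 10.
- 13.79 × 10 = 137.9 nmol/L, which rounds to 138.
- 63.46 × 10 = 634.6 nmol/L, which rounds to 635.

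Both limits reproduce. With M from 362 to 363 the lower limit is 138.1 to 137.7 and the upper limit 635.4 to 633.6 nmol/L.

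**Step 4. Check without assuming M.** The criterion's own numbers imply a molar mass under each reading.

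| Reading of the second unit | From the lower limit | From the upper limit |
|---|---|---|
| nmol/dL (as printed) | 5000 / 138 = 36.2 g/mol | 23000 / 635 = 36.2 g/mol |
| nmol/L | 50000 / 138 = 362.3 g/mol | 230000 / 635 = 362.2 g/mol |

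The two limits agree with each other under either reading, so the digits are consistent and the discrepancy lies in the denominator of the unit. The result does not depend on the exact value of M: the printed ranges would begin to touch only if 138 × M / 1000 ≤ 23, that is, M ≤ 166.7 g/mol.

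**Step 5. Effect on one result.** A result of 400 nmol/L is 40.0 nmol/dL, or 40.0 × 362.46 / 1000 = 14.5 mcg/dL. It lies inside 5-23 mcg/dL, and inside 138-635 if those numbers are read as nmol/L. It lies below 138 nmol/dL, so it falls outside the molar range as printed.

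**The case against.** The arithmetic is not in dispute; the case on the other side is about consequence.

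- **The literal reading points the other way.** The ranges are joined by "or", so a patient at 14.5 mcg/dL meets the first alternative and is eligible. Wrong exclusion needs a reader who uses only the second expression. This stands, and the harm is conditional on that use. But read literally, the "or" would also admit results of about 50-230 mcg/dL, which is another reason to correct the text.
- **The route to error is narrow.** Cortisol is measured by the central laboratory, and nothing else in the documents uses nmol/dL. The documents do not say in which unit screening results reach the sites, but a result in mcg/dL or nmol/L compared with the bare numbers is classified consistently. Someone has to apply or convert to the printed unit to go wrong. This stands too.
- **An edit check is hypothetical.** Neither document describes a programmed cortisol check. That is correct; any such check simply needs to be looked at when the text is fixed.
- **It is a misprint with no analytic effect.** Cortisol has no hypothesis attached, and the intended range can be recovered from the text. This limits how much the point matters, but it does not make the printed limit correct. This is a criterion that decides who enters the trial, not background prose.

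**Conclusion.** The concern holds. Criterion 7 is wrong as written in both places it appears: "5-23 mcg/dL or 138-635 nmol/dL" is not one range, because its two halves differ by a factor of 10 at both limits and do not overlap. The molar numbers match the mass range to rounding only in nmol/L, the unit the SAP already uses for cortisol.

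The conclusion rests on one outside figure, cortisol's molar mass. Any value from 362 to 363 g/mol gives the same answer, and the internal check in Step 4 points the same way.

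The factor of 10 measures the inconsistency in the text, not a demonstrated effect on enrolment. No sample size, power or PK figure depends on it. It should be corrected because it is an eligibility threshold and the correction is nearly free.

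**What to change.** Reconcile the two expressions in criterion 7 of Protocol Section 7.4.2 and of the synopsis so that they describe a single range. State the molar version in nmol/L to match SAP Table 14.1.6 and Listing 16.2.6, with the sponsor confirming the intended range. If an eCRF check or site worksheet carries the cortisol limits, confirm that it uses the corrected unit.

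The cost is one unit correction in two places, by administrative amendment or clarification memo. The SAP and the analysis do not change.
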